11.3 Lost to Follow-Up

A study participant will be considered lost to follow-up if s/he fails to complete both study follow-up assessments and study staff are unable to contact the participant after at least 3 attempts. The following actions must be taken before a participant will be declared lost to follow-up.

- Study staff will attempt to contact the participant, re-send the REDCap survey or reschedule the missed phone-based assessment, and ascertain whether the participant wishes to and/or should continue in the study
- The study staff will make every effort to regain contact with the participant (using text, email, phone call, and/or alternative means of contact).
- Should the participant continue to be unreachable, s/he will be considered lost to follow-up and will be withdrawn from the study.

12. Data & Safety Monitoring

12.1 Overview of Data & Safety Monitoring Plan

This research will include a designated Research/Medical Monitor (RM), a clinician with appropriate psychiatric and medical training and experience reviewing safety outcomes for suicide prevention clinical trials. This research will also include a Data and Safety Monitoring Board (DSMB). The RM will also serve on the DSMB. The DSMB will be convened and managed through the University of Washington's Institute of Translational Health Sciences (UW ITHS).

12.2 Role of the Data & Safety Monitoring Board (DSMB)

The DSMB will review and oversee the following elements:

1. Study enrollment by study site and population (adults, adolescents)
2. Retention of study participants at 6 and 12 months
3. Data completeness and quality
4. Safety outcomes by intervention arm and population (adults, adolescents)
5. Interim analyses to assess whether one intervention is significantly more effective than the other

6. Decisions related to stopping the trial early due to one or more of the elements above

12.3 Safety Outcomes

This protocol considers completed suicide, suicide attempts, and inpatient admission in the context of highly suicidal study participants as expected events. These will be routinely tracked as key safety outcomes. The following safety outcomes will be assessed for each participant at 6 and 12 months and reviewed by the Data and Safety Monitoring Board twice annually to determine whether the rate of safety outcomes differs by intervention arm:

- Death by suicide
- Attempted suicide
- Interrupted or aborted suicide attempt
- Psychiatric hospitalization
- Medical hospitalization related to self-harm or attempted suicide

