 - Outcomes survey includes loneliness, suicide risk, self-harm and suicidal behavior, behavioral health treatment.

12 Month Outcome Assessment – All participants (+ 4 weeks variance window) (REDCap survey link sent via email or text, or phone call)

- 12-Month Outcomes Survey
 - Outcomes survey includes loneliness, suicide risk, self-harm and suicidal behavior, behavioral health treatment, and patient satisfaction.

Assessing Provider Satisfaction (Aim 2)

Providers and staff in study sites will be emailed an invitation to complete a survey during year 1 or 2 of the study. Providers and staff will complete surveys using a REDCap link delivered via email. A statement will be included in the survey invitation email indicating that opening the link and completing the survey constitutes provider/staff consent to participate in the survey. These surveys will be confidential and no personal health information will be collected.

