The C-SSRS is available in a full-length version comprised of 11 yes/no questions plus 7 multiple choice questions and space to collect and record brief narrative explanations. An abbreviated screener version of the C-SSRS consists of 5 yes/no questions related to suicidal ideation and one two-part yes/no question related to suicidal behavior. Both the full-length and screener versions of the C-SSRS are available in a 'lifetime-recent' version (to establish a baseline) and a 'since last contact' version to be administered at follow-up visits. Two versions of the C-SSRS will be used for this study: C-SSRS Lifetime-Recent Screener (given at baseline, in accordance with standard of care at SLHS), and C-SSRS Since Last Contact Screener (given at 6 and 12 months). In addition to using the C-SSRS Screeners at baseline and follow-up, the study will incorporate three items from the full-version of the C-SSRS that are not included in the screener version to measure: (1) Aborted or self-interrupted suicide attempts; (2) interrupted suicide attempts; and (3) actual suicide attempts at baseline, 6, and 12 months. Non-lethal self-harm, lethal means used for attempts or completions, and death by suicide will also be collected. Vital records will be used to measure suicide completion.

In EDs, C-SSRS screening is routinely administered by nurses during triage as standard of care, while in primary care clinics the C-SSRS screener will be self-administered by patients. The C-SSRS delivered as standard of care in either setting will be used as the basis for determining eligibility for completing a safety plan and eligibility for study enrollment. However, in ED settings, the C-SSRS will be re-

administered in a self-complete format for study participants as part of their baseline surveys, from which change in severity of suicidality will be measured when they self-complete the C-SSRS as part of 6 and 12-month outcome surveys.

The two C-SSRS scores collected during the baseline visit in EDs (nurse-administered vs. self-administered) will be compared as a sub-analysis to assess for any systematic differences in score. The results of this sub-analysis may inform future clinical practice as it relates to C-SSRS administration in SLHS EDs and other settings.

Table 3: C-SSRS Screening Tools by Timepoint, SPARC Trial

Timepoint	C-SSRS Assessment Used
Baseline Survey	Lifetime-Recent C-SSRS Screener (6 questions)

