9.2.1 Scoring the C-SSRS

The C-SSRS lifetime-recent screener score is determined based on the highest question number (1-6) to which a participant responds “yes”. For example, a score of 5 would be assigned to a participant who responded “yes” to Question 5 and any or all preceding questions. Please consult *Appendix A* of this protocol for additional C-SSRS scoring criteria. The additional items related to suicide attempts and lethal means will not be included in the C-SSRS score but will be compared across intervention groups.

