12.4 Adverse Events and Serious Adverse Events

This protocol does not include tracking of adverse events (AEs). This protocol does not include real-time tracking of serious adverse events (SAEs) for several reasons. First, as stated above, the most important events that would be defined as SAEs are expected safety outcomes in the context of study participants experiencing suicidality. All deaths of study participants will be reviewed and assessed to determine whether the cause of death is suicide. We do not anticipate any SAEs beyond those listed as safety outcomes above, but unanticipated SAEs that occur will be reviewed by the DSMB and the IRB. Second, this research compares two evidence-based interventions that have been widely studied, have an established safety record, and are already in widespread clinical practice, including within SLHS. These are not experimental, novel, or untested interventions with unknown safety outcomes. Finally, the most important safety question to ascertain in the context of this trial is whether rates of safety outcomes or SAEs are differential across the two intervention groups. Given that the two interventions include different types and frequency of contact with study participants, if the study were to monitor AEs and/or SAEs in real-time, differential rates of ascertainment would be expected. Any attempt to compare rates of AEs or SAEs across intervention groups could be substantially biased due to differential ascertainment. Instead, this protocol will monitor safety outcomes collected at 6 and 12 months as part of routine study outcome assessments through regular DSMB meetings to ensure equal ascertainment of outcomes across intervention groups. This is the most valid and reliable way to review safety data in the context of this pragmatic clinical trial.

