APPENDIX A: C-SSRS Screening Questions & Scoring Criteria

Question #	Domain	Question	Score
1.	Ideation: Wish to be dead	Have you ever wished you were dead or wished you could go to sleep and not wake up?	1
2.	Ideation: Suicidal thoughts	Have you had any actual thoughts of killing yourself?	2
3.	Ideation: Suicidal thoughts with method (without specific plan or intent to act)	Have you been thinking about how you might do this?	3
4.	Ideation: Suicidal intent (without specific plan)	Have you had these thoughts and had some intention of acting on them?	4
5.	Ideation: Suicide intent with specific plan	Have you started to work out or worked out the details of how to kill yourself? Do you intend to carry out this plan?	5
6A. [Lifetime-Recent]	Suicidal Behavior (lifetime)	Have you ever done anything, started to do anything, or prepared to do anything to end your life?	[Not scored at baseline]
6B. [Lifetime-Recent]	Suicidal Behavior (3 mos)	If yes to 6A, Was this within the past 3 months?	6
6. [Since last contact]	Suicidal Behavior (since last contact)	Have you done anything, started to do anything, or prepared to do anything to end your life?	6

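### The by-arm safety list in section 12.3 leaves out self-harm that is neither a suicide attempt nor a cause of admission, although self-harm is surveyed in both arms at 6 and 12 months

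*Protocol*

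**What the plan says.** Section 12.3 lists what is assessed at 6 and 12 months and reviewed by the DSMB twice a year for differences between arms: suicide death, attempts, interrupted or aborted attempts, psychiatric admission, and "Medical hospitalization related to self-harm or attempted suicide". Section 12.2 asks for safety outcomes by arm and separately for adults and adolescents.

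Section 12.4 does not track adverse events and does not follow serious adverse events in real time. Its reason is that the arms differ in contact with participants, so real-time reporting would be uneven. Safety is monitored from the routine 6- and 12-month assessments instead, "to ensure equal ascertainment of outcomes across intervention groups". Outside the list, only unanticipated serious adverse events go to the DSMB.

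On data collection, section 9.2 names three attempt items and then adds: "Non-lethal self-harm, lethal means used for attempts or completions, and death by suicide will also be collected". Section 7 says of the surveys at both time points: "Outcomes survey includes loneliness, suicide risk, self-harm and suicidal behavior". Table 4 has a self-harm entry at 6 and at 12 months, in one row with attempts and completions.

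**The concern.** The trial plans to ask every participant about self-harm at the two times when safety outcomes are reported, but the list that fixes what the DSMB compares between arms admits self-harm only if it leads to medical hospitalization. With adverse events untracked, that list is the main specified by-arm view of harm. If it is followed as written, an imbalance in self-harm short of an attempt or an admission would not be shown to the board during the trial, for adults or adolescents.

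Severity does not explain the omission. Interrupted and aborted attempts are listed, and they need involve neither injury nor admission. The ascertainment argument of section 12.4 does not explain it either, because survey items asked of both arms on the same schedule are the kind of data that section prefers.

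**Working it through.** **Check of the list.** Take self-harm that is not an actual, interrupted or aborted attempt and leads to no psychiatric or medical admission, and compare it with each item in section 12.3.

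| Item in 12.3 | Covers it? |
|---|---|
| Suicide death | No |
| Attempt | No |
| Interrupted or aborted attempt | No |
| Psychiatric admission | No |
| Medical admission for self-harm or attempt | No |

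It matches 0 of 5.

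**Check of other routes to by-arm review.**

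- Section 12.2 refers to safety outcomes, which 12.3 defines, so it adds nothing.
- Section 12.4 excludes adverse events.
- Section 12.5 has the research/medical monitor review how staff respond to participants in crisis. It calls for no comparison of event counts by arm.
- Appendix A: the follow-up C-SSRS behavior item asks "Have you done anything, started to do anything, or prepared to do anything to end your life". It is confined to acts meant to end life.
- Section 9.2.1 says the "additional items related to suicide attempts and lethal means will not be included in the C-SSRS score but will be compared across intervention groups". Self-harm is not named, and the comparison is not assigned to the DSMB.
- Section 6.4 gives the DSMB safety data on all enrolled participants. That defines a population, not the outcomes to tabulate.

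**Check of availability.** Sections 7 and 9.2 and Table 4 together place self-harm data in both arms at 6 and 12 months. Table 1 schedules safety reporting at the same two times.

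**How precise an added row could be.** The protocol states no figure on this, so there is none to reproduce, and no self-harm rate is assumed.

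- Inputs: 592 adolescents, 790 adults and up to 30% dropout (section 14.2). Allocation of 1:1 is an assumption.
- Observed per arm: adolescents 592 × 0.7 / 2 = 207.2; adults 790 × 0.7 / 2 = 276.5.
- The 95% half-width for a difference in proportions is largest when both proportions are 0.5: 1.96 × √(2 × 0.25 / n).
- Adolescents: 1.96 × √(0.5 / 207.2) = 0.0963, or 9.6 percentage points.
- Adults: 1.96 × √(0.5 / 276.5) = 0.0833, or 8.3 points.
- With full retention (592 / 2 = 296 and 790 / 2 = 395 per arm): 0.0806 and 0.0697, or 8.1 and 7.0 points.

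These are upper bounds at the end of follow-up. At earlier DSMB reviews fewer participants have been followed, and the bound is wider.

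**The case against.** The strongest reply is that the list has a coherent scope. Each item is either suicidal behavior or an admission. Self-harm without suicidal intent and without admission is neither, would sit at adverse-event level, and the protocol says openly that it does not track adverse events. Collecting an item does not make it a safety outcome; loneliness is collected at the same visits. On this view nothing is contradicted. That last part stands: this is an incomplete list, not an inconsistency. The scope argument is weaker, because 12.3 already treats self-harm as a safety matter once it leads to medical admission, and the survey data meet the protocol's own condition of equal ascertainment.

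Three further points stand as limits.

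- Section 9.2 says non-lethal, not non-suicidal. Self-harm is listed apart from the three attempt items there, but Table 4 puts attempts, completions and self-harm in one row, sourced mainly from a survey named for suicide attempts. The survey is not shown, so a separate count of non-attempt self-harm is an inference.
- Because of that survey name, the comparison promised in 9.2.1 might be meant to include self-harm. Even so, it is not assigned to the DSMB.
- The charter and reporting tables that the DSMB reviews at the outset (section 17.16.1) are not shown and may already contain such a row.

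It is also fair that the precision bound would apply to any yes/no outcome at these sample sizes. It describes what an added row could show, not the size of any harm missed.

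**Conclusion.** The concern holds as a minor gap in safety monitoring. As written, section 12.3 and the sections around it give the DSMB no by-arm count of self-harm outside attempts and admissions, although self-harm data are due from both arms at both follow-up times. Suicide deaths, attempts of all three kinds and admissions remain monitored.

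No missed excess is claimed. The conclusion rests on two readings: that the survey records self-harm beyond attempts, and that the unseen DSMB documents do not already cover it. Confidence is therefore moderate, and the change is optional but worthwhile.

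**What to change.** Add to section 12.3 and to the DSMB tables one descriptive row, by arm and by age group, for non-lethal self-harm not classed as an actual, interrupted or aborted attempt, taken from the existing 6- and 12-month surveys. Keep psychiatric and medical admissions as separate rows. If the survey cannot separate self-harm from attempts, show any reported non-lethal self-harm beside the attempt rows, and note that the rows may overlap and should not be summed. If the charter or tables already include the row, cite them in 12.3.

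No new data collection is needed. The cost is one more unpowered comparison for the board to weigh, so the row should be labelled descriptive.

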12.4 Adverse Events and Serious Adverse Events

This protocol does not include tracking of adverse events (AEs). This protocol does not include real-time tracking of serious adverse events (SAEs) for several reasons. First, as stated above, the most important events that would be defined as SAEs are expected safety outcomes in the context of study participants experiencing suicidality. All deaths of study participants will be reviewed and assessed to determine whether the cause of death is suicide. We do not anticipate any SAEs beyond those listed as safety outcomes above, but unanticipated SAEs that occur will be reviewed by the DSMB and the IRB. Second, this research compares two evidence-based interventions that have been widely studied, have an established safety record, and are already in widespread clinical practice, including within SLHS. These are not experimental, novel, or untested interventions with unknown safety outcomes. Finally, the most important safety question to ascertain in the context of this trial is whether rates of safety outcomes or SAEs are differential across the two intervention groups. Given that the two interventions include different types and frequency of contact with study participants, if the study were to monitor AEs and/or SAEs in real-time, differential rates of ascertainment would be expected. Any attempt to compare rates of AEs or SAEs across intervention groups could be substantially biased due to differential ascertainment. Instead, this protocol will monitor safety outcomes collected at 6 and 12 months as part of routine study outcome assessments through regular DSMB meetings to ensure equal ascertainment of outcomes across intervention groups. This is the most valid and reliable way to review safety data in the context of this pragmatic clinical trial.

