6.4 Populations for Analyses

Analyses will be completed using the following populations:

1. **Intention to Treat (ITT) Analytic Population:** Data for all participants that complete study enrollment will be included in this dataset.
2. **Safety Analysis Population:** The dataset shared with the Data & Safety Monitoring Board for safety analysis will include data for all participants who completed study enrollment (e.g., the ITT Analytic Population Dataset).
3. **Per-Protocol Analysis Population:** Data for a subset of participants who were retained for the duration of the study and completed the minimum assigned intervention (e.g. received at least one phone call (SPI+), or were sent at least 4 caring contacts (SP+CC)).
4. **Additional Populations:** Additional datasets may be developed to complete sensitivity analyses, for example, where missing data have been imputed using different techniques.

7. Study Procedures

Pre-Consent – All participants (All activities are standard of care)

- C-SSRS screening for suicide risk at clinic or ED visit
- Development of safety plan or a connection and support plan

Baseline / Enrollment Visit – All participants (During/following clinic or ED visit)

- Study enrollment and informed consent
- Baseline Survey
 - Baseline survey includes questions related to demographics, socioeconomic status, gender identity, sexuality, religion, drug and alcohol use, quality of life, loneliness, self-harm and suicidal behavior.

Follow-Up Intervention – SPI+ participants

- Follow-up phone calls from the Hotline
 - 1 call within 72 hours of study enrollment to connect with the participant.
 - Series of 1-6 phone calls, based on participant's preference.
 - See *Description of Interventions*.

Follow-Up Intervention – SP+CC participants

- Follow-up phone call and caring text or email messages from the Hotline
 - 1 call within 72 hours of study enrollment to connect with the participant.
 - 25 personalized caring text or email messages sent according to a standardized schedule over a 12-month period.
 - See *Description of Interventions*.

2-Week Patient Satisfaction Survey – All participants (REDCap survey link sent via text or email)

- Patient satisfaction survey related to intervention received

6 Month Outcome Assessment – All participants (+ 4 weeks variance window) (REDCap survey link sent via email or text, or phone call)

- 6-Month Outcomes Survey

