11.1 Discontinuation of Study Intervention / Experimental Manipulation

Participants may choose to discontinue the follow-up intervention by contacting study staff. When a participant discontinues the intervention but remains in the study, remaining study procedures will be completed as indicated in the study protocol.

Data to be collected at the time of study intervention discontinuation will include the following:

- The date of discontinuation of the intervention
- The reason(s) for discontinuing the intervention (if available)

The participant will be eligible to complete follow-up surveys, even if they are not participating in the assigned intervention.

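### Section 12.4 says that collecting safety outcomes at 6 and 12 months ensures equal ascertainment between arms, but a shared schedule equalises the opportunity to report, not the response

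*Protocol*

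**What the plan says.** Section 12.3 lists five safety outcomes: suicide death, attempt, interrupted or aborted attempt, psychiatric hospitalization, and medical hospitalization related to self-harm or an attempt. They are assessed at 6 and 12 months and reviewed by the DSMB twice a year "to determine whether the rate of safety outcomes differs by intervention arm".

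Section 12.4 declines real-time tracking because the arms differ in type and frequency of contact, which would make ascertainment differ. Events are instead collected "as part of routine study outcome assessments through regular DSMB meetings to ensure equal ascertainment of outcomes across intervention groups".

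Other parts of the protocol bear on whether that claim holds:

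- **Who is in the data (6.4).** "The dataset shared with the Data & Safety Monitoring Board for safety analysis will include data for all participants who completed study enrollment". No denominator for a safety rate is stated.
- **Who drops out (11.3).** A participant is lost who "fails to complete both study follow-up assessments and study staff are unable to contact the participant after at least 3 attempts"; that person "s/he will be considered lost to follow-up and will be withdrawn from the study". Section 14.2 allows for up to 30% dropout.
- **Who stays (11.1).** After stopping the intervention, "The participant will be eligible to complete follow-up surveys, even if they are not participating in the assigned intervention".
- **Sources (Table 4, 9.2).** Attempts, completion and self-harm have the survey, vital records and EPIC. ED return for suicidality also has EDIE and claims. Interrupted and aborted attempts are added C-SSRS items with no record source named. Neither hospitalization outcome has a row.
- **Oversight (12.2).** Safety outcomes are reviewed by arm. Retention and data completeness are also reviewed, but not stated to be by arm.

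**The concern.** Section 12.4 treats a common collection schedule as enough to make ascertainment equal. That requires similar proportions of each arm to complete the assessments, and nothing in the design secures this. Contact differs for most of the year: SP+CC participants are sent 25 messages over 12 months (10.4), while SPI+ calls are generally scheduled to day 90 and may end sooner (10.2). A difference in willingness to answer surveys is therefore plausible, though the protocol gives no evidence that it will occur.

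If completion does differ, an outcome known only by survey is under-counted more in the arm with more missed surveys. Where the rate is taken over everyone enrolled, that arm looks safer than it is and the better-retained arm looks less safe. Section 12.4 itself ranks the between-arm comparison as the main safety question, and section 12.2 gives the DSMB stopping decisions based on it. A DSMB that takes equal ascertainment as given would have no reason to check completion by arm before reading a difference as real, or an absence of difference as reassuring.

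**Working it through.** Section 12.4 states no figure to reproduce, so the check asks how far the comparison could move when the true risk is the same in both arms.

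**Inputs from the protocol.** Total sample 1,382 (790 adults, 592 adolescents); dropout allowance 30%, hence 70% average retention; two-sided alpha 0.05.

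**Assumptions (not in the protocol).** Allocation 1:1, so 1,382 / 2 = 691 per arm. Retention 75% vs 65% or 80% vs 60%, both averaging 70%. True 12-month risk p = 10% in both arms, with 10% to 30% for the significance check. Record capture s is the share of non-responders' events found in records, from 0 to 1. Relative risk k compares those lost with completers, at 1 or 2.

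**All enrolled as denominator, non-responders having the same risk.** Apparent rate = p × [r + (1 − r) × s], where r is the arm's retention. Ratios are less-retained over better-retained arm; p cancels.

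| Retention | s | Rates at p = 10% | Ratio |
|---|---|---|---|
| 75 / 65 | 0 | 7.5% vs 6.5% | 0.87 |
| 75 / 65 | 0.5 | 8.75% vs 8.25% | 0.94 |
| 75 / 65 | 0.8 | 9.5% vs 9.3% | 0.98 |
| 80 / 60 | 0 | 8.0% vs 6.0% | 0.75 |
| 80 / 60 | 0.5 | 9.0% vs 8.0% | 0.89 |
| 80 / 60 | 0.8 | 9.6% vs 9.2% | 0.96 |
| any | 1 | 10% vs 10% | 1.00 |
| 70 / 70 | any | equal | 1.00 |

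For example, 75 / 65 with s = 0.5: 0.10 × (0.75 + 0.25 × 0.5) = 8.75%; 0.10 × (0.65 + 0.35 × 0.5) = 8.25%; 8.25 / 8.75 = 0.94.

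**Completers as denominator, survey events only.** Completer rate = p / [r + (1 − r) × k].

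- k = 1: 10% in both arms, ratio 1.00 at any retention gap.
- k = 2, 75 / 65: 0.10 / 1.25 = 8.0% vs 0.10 / 1.35 = 7.4%, ratio 0.93.
- k = 2, 80 / 60: 0.10 / 1.20 = 8.3% vs 0.10 / 1.40 = 7.1%, ratio 0.86.

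**Chance of a false p < 0.05, all enrolled.** For a pooled two-proportion z-test with apparent difference d and standard error SE = √[2 × p̄ × (1 − p̄) / 691], where p̄ is the mean of the two apparent rates, the chance is Φ(d/SE − 1.96) + Φ(−d/SE − 1.96).

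- Survey-only, 75 / 65, p = 20%: 15% vs 13%, SE = √(2 × 0.14 × 0.86 / 691) = 0.0187, d/SE = 1.07, chance 19%. It is 11% at p = 10% and 28% at p = 30%.
- Survey-only, 80 / 60: 57% at p = 20%, and 31% to 78% across p = 10% to 30%.
- With s = 0.5 and p = 20%: 8% at 75 / 65 and 17% at 80 / 60.
- With s = 0.8 and p = 20%: 5% and 7%, near nominal.

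**The case against.** The strongest reply is that the protocol does not rely on surveys alone. Table 4 gives attempts and self-harm EPIC and vital records beside the survey, section 9.2 uses vital records for suicide completion, section 12.4 reviews every death, and section 17.13 adds National Death Index data. Suicide death is therefore largely outside the problem, and for attempts the survey-only rows are an upper bound for a given retention gap when non-responders share the same risk. This stands.

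A reader might also infer that the plan counts lost participants as event-free and so creates a false safety difference. The documents do not support that:

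- Section 6.4 says whose data enter the dataset, not how a rate is formed; that may sit in the statistical analysis plan or the DSMB tables.
- Being lost requires missing both assessments and at least three failed contact attempts. Someone who misses month 6 can still report at month 12 on a since-last-contact instrument.
- Bias needs both unequal completion and incomplete record capture, or, with completers as denominator, loss related to risk. No retention by arm is given.

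Nor does section 12.4's worry about real-time contact carry over directly. SLHS, not the Hotline, collects the surveys, with the same retention methods and payments described for all participants (6.3, 17.7). Unequal completion is possible, not demonstrated.

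The DSMB's review of retention and completeness is a partial safeguard, but it is not stated to be by arm. Finally, Table 4 is introduced as covering the primary analysis, so a missing hospitalization row is weaker evidence than it looks. Even so, section 12.3 names no source for those outcomes either.

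None of this makes the claim of ensured equality correct.

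**Conclusion.** The point holds in a limited form. Section 12.4 claims a property that a common schedule does not have: ascertainment is equal only if completion is similar in both arms or records fill the gap. The exposed outcomes are interrupted or aborted attempts, attempts not visible in EPIC, and the two hospitalization outcomes.

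Under the assumed 75% versus 65% retention, the distortion over all enrolled runs from a ratio of 0.87 (survey only) through 0.94 to 0.98 (half and 80% capture). Among completers it is 1.00 or 0.93, depending on whether loss is related to risk. It vanishes with equal retention when those lost have the same relative risk in both arms, or with complete capture. A wider gap makes it material. These figures rest on assumed retention, risk and capture; the direction and the dependence do not. What is established is that the comparison can be biased and that the text says otherwise, not that it will be. The change is worth making because the comparison is central to safety oversight and the remedy is cheap.

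**What to change.** In sections 12.3 and 12.4 and Table 4:

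1. Name EPIC, the EDIE/ED dashboard and claims as sources for attempts and both hospitalization outcomes, and vital records for deaths. Query them identically for every enrolled participant, including those lost to follow-up, unless record access is refused.
2. Report survey-reported events, including interrupted or aborted attempts, separately, with that time point's survey completers as denominator.
3. Give the DSMB survey completion by arm at 6 and 12 months beside the safety tables.
4. Replace the claim that equal ascertainment is ensured with a statement that it depends on similar completion by arm.

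The cost is protocol wording plus an extension of record queries already planned for ED return and service uptake (9.3.2 to 9.3.4). Two limits remain. Records cannot be relied on for interrupted or aborted attempts. Section 9.3.4 expects incomplete data on care outside SLHS, and because SPI+ calls support treatment engagement, the arms could differ in where care is sought and so in capture. Record-based and survey-based results should therefore both be shown, with neither treated as free of bias.
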